This study will be a randomized, controlled superiority trial to evaluate a hospital-wide initiative to improve counseling for postpartum women who experienced HDP during their pregnancy or in the immediate postpartum period. Hypotheses: 1. We hypothesize that the prompt will increase the proportion of women counseled on transitioning care to a primary care provider or cardiologist after pregnancy (primary outcome). 2. We hypothesize that the provider nudge will increase the proportion of women attending a preventative care visit within 6 months of delivery as assessed by chart review and patient surveys. The HSM daily log generated through the Way to Health platform will be used to generate lists of patients who eligible for the study. For each eligible woman, the date of and obstetric care provider for her postpartum visit will be recorded within 3 weeks of delivery. Patients will then be randomly assigned to a control group with no intervention (usual care through HSM) or the intervention group (physician nudge) using simple 1:1 randomization through the Way to Health Platform. If a woman is randomized to the intervention arm, her obstetric care provider for her postpartum visit will receive a staff message in Epic (Penn Chart) that his/her patient has an upcoming postpartum visit. The message will be sent 1 week before the scheduled visit. The message will have patient-specific information including hypertensive diagnosis, blood pressure medication(s), gestational diabetes diagnosis, and primary care provider as listed in the Epic banner. The message will also have dot phrases for recommended counseling and contact information for UPHS primary care and cardiology providers. There will be a dot phrase recommending follow-up with primary care or cardiology; counseling on risk of future CVD; and recommending aspirin in a future pregnancy. A web-based survey will be distributed to all women in the study 6 months after delivery through the Way to Health platform. The survey will assess attendance at a preventative care visit, social determinants of health, health status, and insurance status after delivery. Demographic characteristics, medical and obstetric history, hypertensive disorder, laboratory test results (platelet count, creatinine, liver function tests, urine protein, total cholesterol, triglycerides, LDL-C, HDL-C, glucose, hemoglobin A1c), blood pressure measurements, height, weight, and office visits within 6 months of delivery will be abstracted from the EMR. We will perform detailed abstraction of counseling at the postpartum visit and additional office visits within 6 months of delivery focusing on 1) health maintenance 2) hypertension, or 3) cardiovascular risk reduction. Two reviewers will assess counseling at each visit. We will obtain data on obstetric care providers including level (resident physician, attending physician, nurse practitioner, physician assistant, or certified nurse midwife), gender, and years in practice from publicly available databases or websites online.

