A flowsheet of patient participation is attached. Subjects will be identified through the HSM daily log. A waiver of informed consent is requested for the intervention portion of this study. At 30 days after discharge, all participants, regardless of study arm will receive the following message "Hello from Heart Safe Motherhood! We hope you are doing well. Dont forget to follow-up with your primary or heart doctor in the next 2-4 weeks. If you were given an appointment, make sure to keep it. If you want to make an appointment with a heart doctor focused on women's health, call [contact]. Have a great day!" At 6 months postpartum, women will receive a secure text message through the Way To Health platform. "We are trying to understand how women with high blood pressure or preeclampsia stay healthy after delivery. Respond yes if you are willing to complete a survey. You will receive \$5 for participating." If she responds yes, she will receive a survey link integrated with Way To Health. Patient information will be obtained from the electronic medical record including demographic characteristics, medical and obstetric history, hypertensive disorder, laboratory test results (platelet count, creatinine, liver function tests, urine protein, total cholesterol, triglycerides, LDL-C, HDL-C, glucose, hemoglobin A1c), blood pressure measurements, height, weight, and office visits within 6 months of delivery. We will perform detailed abstraction of counseling at the postpartum visit and additional office visits within 6 months of delivery focusing on 1) health maintenance 2) hypertension, or 3) cardiovascular risk reduction. Two reviewers will assess counseling at each visit (from the discharge summary and after visit summary). We will obtain data on obstetric care providers including level (resident physician, attending physician, nurse practitioner, physician assistant, or certified nurse midwife), gender, and years in practice from publicly available databases or websites online.

The following documents are currently attached to this item:

There are no documents attached for this item.

Deception

Does your project use deception?

No

International Research

Are you conducting research outside of the United States?

No

Analysis Plan

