We hypothesize that a provider nudge will increase the proportion of women who are counseled about 1) transitioning care and 2) CVD risk after pregnancy complicated by HDP. This is designed as a superiority trial. We hypothesize that the provider nudge will lead to improved follow-up with continuity care providers. Primary efficacy endpoint: 1. Documentation of counseling about transitioning care to a continuity care provider (primary care or cardiology) at the postpartum visit. Secondary efficacy endpoints: 1. Documentation of CVD risk at the postpartum visit. 2. Attendance at a primary care or cardiology visit for preventative care within 6 months of delivery. Chi square or Fishers exact test will be used to compare categorical data. T-test will be used to compare parametric data. Mann-Whitney U test will be used to compare non-parametric data. Univariate comparisons will be made between exposure (intervention) and outcome. Proportion and relative risk (95% CI) will be presented for primary and secondary outcomes. Multivariable logistic regression models will be created to control for potential confounders. Outcomes will be analyzed by the intention to treat principle. Our threshold for statistical significance will be two-side with alpha 0.05. Exploratory analyses: Primary and secondary outcomes will be analyzed by race (Black vs. Non-Black) based on data that HSM reduced racial disparities in blood pressure ascertainment outcomes. We will explore whether there is an interaction of race with regards to counseling and follow-up. We will also assess time trends in counseling over the study period.

The following documents are currently attached to this item:

There are no documents attached for this item.

Data confidentiality

- Paper-based records will be kept in a secure location and only be accessible to personnel involved in the study.**
- Computer-based files will only be made available to personnel involved in the study through the use of access privileges and passwords.**
- Prior to access to any study-related information, personnel will be required to sign statements agreeing to protect the security and confidentiality of identifiable information.**
- Wherever feasible, identifiers will be removed from study-related information.**

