- A Certificate of Confidentiality will be obtained, because the research could place the subject at risk of criminal or civil liability or cause damage to the subject's financial standing, employability, or liability.**
- A waiver of documentation of consent is being requested, because the only link between the subject and the study would be the consent document and the primary risk is a breach of confidentiality. (This is not an option for FDA-regulated research.)**
- Precautions are in place to ensure the data is secure by using passwords and encryption, because the research involves web-based surveys.**
- Audio and/or video recordings will be transcribed and then destroyed to eliminate audible identification of subjects.**

Subject Confidentiality

Computer-based files will only be made available to personnel involved in the study through the use of access privileges and passwords. Wherever feasible, identifiers will be removed from study-related

information. Precautions are already in place to ensure the data are secure by using passwords and HIPAA-compliant encryption. Data on patients will be obtained from Epic and patient-completed surveys. Any information that is obtained will be used for research purposes only. Information on patients will only be disclosed within the study team and to the patients obstetric care provider. All study staff will be reminded of the confidential nature of the data collected and contained in these databases. All members that access data must complete HIPAA training including secure data transfer, passwords, computer security habits and knowledge of what constitutes misuse or inappropriate use of the server. Only trained study staff will have access to the code that links the unique identifier to the subjects identity. Electronic data will be stored on secure, password-protected firewalled servers at the University of Pennsylvania. Data collected for this study will be stored in REDCap and the WayToHealth platform. Linkage to PHI will be stored until study analysis and publication completion, and then will be destroyed.

Sensitive Research Information*

Does this research involve collection of sensitive information about the subjects that should be excluded from the electronic medical record?

No

Subject Privacy

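### Six-month attendance may be captured better in the nudge arm, because it is read from the Epic chart plus a voluntary survey while only the nudge message supplies UPHS contacts

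*Combined protocol and SAP*

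**What the plan says.** The Analysis Plan lists as a secondary efficacy endpoint "Attendance at a primary care or cardiology visit for preventative care within 6 months of delivery". It is not restricted to UPHS. Hypothesis 2, in the Design section, says attendance will be assessed "as assessed by chart review and patient surveys".

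- **Chart.** The Design section states that "office visits within 6 months of delivery will be abstracted from the EMR".
- **Survey.** "A web-based survey will be distributed to all women in the study 6 months after delivery through the Way to Health platform". It is voluntary: the text message in Procedures reads "Respond yes if you are willing to complete a survey", with a $5 payment. No expected response is given.
- **Other sources.** None is named. Subject Confidentiality says: "Data on patients will be obtained from Epic and patient-completed surveys".
- **The nudge.** In the intervention arm only, the provider's message includes "contact information for UPHS primary care and cardiology providers". The same message shows the woman's own primary care provider as listed in Epic.
- **Both arms.** Thirty days after discharge, every participant gets a text reminding her to see her primary or heart doctor, with a heart-doctor contact.

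The Analysis Plan specifies chi-square or Fisher tests, relative risks and logistic regression by intention to treat. It gives no rule for combining chart and survey, for survey non-response, or for visits outside UPHS.

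**The concern.** Randomization balances the women but not how completely their visits are found. The chart can be read for every woman. A visit the chart does not show is found only if she answers the survey. The intervention names providers in the health system whose chart supplies the outcome. If it changes where some women go, but not whether they go, recorded attendance rises in the nudge arm alone.

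Attendance is the only listed outcome that measures what patients do afterwards. The others measure provider documentation or use of the prompt. A relocation of care could therefore be reported as improved follow-up.

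**Working it through.** **The plan's own figure.** The 222 in the Accrual section is for the primary outcome (21% v 40%, 80% power, two-sided 0.05, 20% not attending the postpartum visit). Without pooling the variance, n per arm = (1.960 + 0.842)² × (0.21×0.79 + 0.40×0.60) / 0.19² = 88.3, and 2 × 88.3 / 0.8 = 220.6. Rounding up to 89 per arm gives 222.5, so the stated figure is reproduced. No sample size or power is given for attendance.

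**Inputs for attendance**
- From the documents: 222/2 = 111 per arm; two-sided alpha 0.05; counseling 21% v 40%; fewer than one third of HSM women with a preventative visit in the year after delivery (Background).
- Assumed: true attendance p = 30% in both arms; in-system share of attenders u; survey response r; the chart finds all UPHS visits and no outside visits; outside visits are found only among responders; a woman with no recorded visit counts as a non-attender.

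**Formula.** Observed attendance = p × [u + (1 − u) × r]. The spurious difference is p × (u_nudge − u_control) × (1 − r). It is zero if place of care does not shift or if every outside visit is recovered (r = 1).

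**A shift tied to the plan's counseling effect.** The planned effect adds 40% − 21% = 19% of women counseled. Suppose half of control attenders go outside, counseling is independent of attendance, and every newly counseled woman who would have gone outside switches. The in-system share then rises by 0.19 × 50% = 9.5 points, from 50% to 59.5%.
- r = 0.2: control 0.30 × (0.50 + 0.50×0.2) = 18.0%; nudge 0.30 × (0.595 + 0.405×0.2) = 20.3%; difference 2.3 points.
- r = 0.4: control 0.30 × (0.50 + 0.50×0.4) = 21.0%; nudge 0.30 × (0.595 + 0.405×0.4) = 22.7%; difference 1.7 points.

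**Results.** The false-positive rate is the rejection probability of the pooled two-proportion test (normal approximation) at 111 per arm.

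| In-system share, control → nudge | Response | Observed, control v nudge | Difference | False-positive rate |
|---|---|---|---|---|
| 50% → 59.5% | 40% | 21.0% v 22.7% | 1.7 points | 6.1% |
| 50% → 59.5% | 20% | 18.0% v 20.3% | 2.3 points | 7.2% |
| 60% → 70% | 40% | 22.8% v 24.6% | 1.8 points | 6.1% |
| 50% → 70% | 20% | 18.0% v 22.8% | 4.8 points | 14% |
| 50% → 80% | 20% | 18.0% v 25.2% | 7.2 points (RR 1.40) | 25% |

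**How far the larger rows can be reached.** With half of attenders outside and 40% counseled in the nudge arm, at most 0.40 × 50% = 20 points can move through counseling. The 50% → 70% row therefore needs every counseled outside-goer to switch, and 50% → 80% exceeds that ceiling. If only half of the newly counseled outside-goers switched, the shift would be 4.75 points and the spurious difference about 1 point (0.30 × 0.0475 × 0.8 = 1.1; × 0.6 = 0.9).

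**The case against.** A reader might infer that visits are certain to be captured better in the nudge arm. The documents do not support that.

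- Nothing in them says the nudge changes where women go. The message goes to the provider, who is free to ignore it, and its suggested wording recommends primary care or cardiology without naming a system.
- It also shows the woman's existing primary care provider, who may be outside UPHS.
- The 30-day text goes to both arms, so direct prompting of patients is equal. Controls also have UPHS postpartum visits, with providers who may already know these contacts.
- That Epic shows only UPHS visits is an inference. So is scoring a woman with no recorded visit as a non-attender, since the plan states no rule.
- The survey goes to everyone and is itself the means of finding outside visits. Its content is not in the documents, so it may already ask about site.

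These points stand, and they reduce the likely contrast. They do not remove it. The UPHS primary care contacts are still supplied in one arm only, the survey is optional, and nothing in the analysis separates relocated care from additional care. Using a survey alongside the chart also suggests that the chart alone was not thought sufficient.

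**Conclusion.** The concern holds as a possibility that the plan leaves unchecked. If the nudge moves visits into UPHS and unrecorded visits count as non-attendance, the error favours the nudge. A shift in line with the planned counseling effect gives about 2 points and a false-positive rate of 6% to 7% against the nominal 5%. That rests on 30% true attendance in both arms, half of control attenders seen outside UPHS, 20% to 40% survey response, and a chart blind to outside visits. The documents supply none of these, so the true size cannot be determined.

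A reader might take the 14% or 25% rows as the expected error. They need in-system shifts of 20 and 30 percentage points with 20% response, which is at or beyond what the planned counseling effect allows.

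This is a secondary outcome in a trial the Abstract calls a pilot. The primary outcome, documented counseling at the UPHS postpartum visit, is not touched, and neither is the sample size.

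**What to change.** 1. For every qualifying visit, record the source (chart or survey) and the site (UPHS or outside).
2. Make sure the 6-month survey asks whether the visit was at Penn. Once the surveys are complete, the site of outside visits cannot readily be recovered.
3. State in the Analysis Plan how chart and survey are combined.
4. Report survey response by arm, and present chart-only (UPHS), survey-responder and combined attendance by arm.
5. Add a sensitivity analysis in which survey non-responders without a charted visit are not treated as known non-attenders.
6. If the difference is confined to UPHS visits, describe it as in-system attendance, not as improved attendance overall.

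Imputation or weighting need not be made the main analysis. Nor should a claim be made conditional on the survey-responder result: at 20% to 40% response that subset is about 22 to 44 women per arm (0.2 × 111 and 0.4 × 111), self-selected and too few for its direction to be reliable.

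The cost is one survey item, one abstraction field, modest analysis work, and a wider interval in the sensitivity analysis.

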
Other Sites

No other sites

Protocol

Abstract

Hypertensive disorders of pregnancy (HDP) are stress tests which may identify women at high risk of future cardiovascular disease (CVD), the leading cause of death among women. Given the public health impact of HDP and CVD, there is a compelling need to identify scalable interventions to improve preventative care among women who have risk identified during pregnancy. We will examine the effects of delivering electronic prompts to obstetric care providers (nudge) on transitions of care in the postpartum period. We will conduct a pilot randomized trial to evaluate whether this nudge intervention will improve postpartum counseling and lead to greater follow-up with preventative care providers among women with HDP. **Objectives**

Overall objectives

The objective of the study is to evaluate the effect of a hospital-wide initiative using electronic prompts to encourage physicians to transition care for women with HDP to continuity care providers in accordance with national society guidelines.

Primary outcome variable(s)

The primary outcome measure is documentation of counseling about transitioning care to a continuity care provider (primary care or cardiology) at the postpartum visit.

Secondary outcome variable(s)

Secondary outcomes include 1. Electronic prompts opened by obstetric care providers within 1 week of receipt. 2. Documentation of CVD risk at the postpartum visit. 3. Use of scripted dot phrases (available in Epic) for counseling on transitions of care and CVD risk in the postpartum note. 4. Attendance at a primary care or cardiology visit for preventative care within 6 months of delivery.

Background

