HDP. A significant proportion of women with HDP do not see a preventative care provider (primary care, cardiology) in the months after delivery.¹⁰⁻¹² Black women are particularly vulnerable to being lost to follow-up after complicated pregnancy.^{10,11} The HSM program is an innovative, patient-centered program that monitors postpartum blood pressure remotely using a text-based interface. It is supported by the Way to Health platform. HSM improves blood pressure management in the two weeks after delivery and eliminates racial disparities in blood pressure ascertainment during that time.^{13,14} However, enrollment in HSM did not improve follow-up in the year after delivery, with less than 1/3 of women having a preventative care visit.¹⁵ Poor follow-up is likely multifactorial, but may be driven by inadequate patient counseling in the postpartum period. Among women enrolled in HSM, only 21% of women were counseled on follow-up with primary care and only 4% were counseled on CVD risk at their postpartum visits based on chart review.¹⁶ Nudges are effective for changing medical decision-making and improving clinical outcomes. Nudges utilize concepts from behavioral economics to subtly change the decision-making environment to facilitate evidence-based care and can be delivered to patients, providers, or both.¹⁷ Examples of nudges include electronic prompts to order cancer screening and electronic defaults that guide ordering practices.¹⁸ Nudges are low cost, scalable using Electronic Medical Record (EMR) systems, and improve rates of preventative services including influenza vaccination, referral to mammography, and statin prescription for CVD prevention.¹⁹⁻²²

References:

1. American College of Obstetricians and Gynecologists; Task Force on Hypertension in Pregnancy. Executive summary: hypertension in pregnancy. *Obstet Gynecol* 2013;122:1122-31.

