Sample size calculations were based on the assumption that 21% of patients in usual care and 40% of patients receiving a provider nudge would have documentation about transitioning care. A sample size of 222 patients (randomized 1:1) would provide 80% power to detect this difference assuming 20% of patients will not attend their postpartum visit. Approximately 100 women are enrolled in HSM each month at Pennsylvania Hospital. We anticipate that over 90% of those women receive prenatal care at a UPHS practice (n=90 per month), and at least 80% will attend a postpartum visit (n=72). We thus anticipate that 222 women could be enrolled in 3-4 months, allowing for 6-month follow-up during the grant period.

Key inclusion criteria

1. At least 18 years old. 2. Have a diagnosis of HDP during delivery admission or have a diagnosis made at time of evaluation in the Perinatal Evaluation and Treatment Unit after discharge from the delivery admission. HDP diagnoses are based on criteria from the American College of Obstetricians and Gynecologists (ACOG). 3. Enrolled in HSM at Pennsylvania Hospital. 4. Have a postpartum visit with a UPHS provider scheduled 4-12 weeks after delivery.

Key exclusion criteria

1. Women diagnosed with chronic hypertension (CHTN) without superimposed pre-eclampsia (PEC).

Vulnerable Populations

Children Form

Pregnant women (if the study procedures may affect the condition of the pregnant woman or fetus) Form

Fetuses and/or Neonates Form

Prisoners Form

Other x None of the above populations are included in the research study

The following documents are currently attached to this item:

There are no documents attached for this item.

Populations vulnerable to undue influence or coercion

This is a hospital-wide initiative which will equally include all postpartum women in HSM who do not meet exclusion criteria.

Subject recruitment

The HSM daily log generated through the Way to Health platform will be used to generate lists of patients who eligible for the study. For each eligible woman, the date of and obstetric care provider for her postpartum visit will be recorded within 3 weeks of delivery.

Will the recruitment plan propose to use any Penn media services (communications, marketing, etc.) for outreach via social media avenues (examples include: Facebook, Twitter, blogging, texting, etc.) or does the study team plan to directly use social media to recruit for the research?

No

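### The nudge supplies chart text matching the primary endpoint and reviewer masking is not stated: give reviewers arm-free charts and limit the claim to documented counseling

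*Combined protocol and SAP*

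**What the plan says.** **Endpoint.** In the Objectives section, the plan reads: "The primary outcome measure is documentation of counseling about transitioning care to a continuity care provider (primary care or cardiology) at the postpartum visit". The Analysis Plan repeats this definition. The Accrual section sizes the trial on the same quantity: "21% of patients in usual care and 40% of patients receiving a provider nudge would have documentation about transitioning care".

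**Hypothesis.** Study Design, Design, states Hypothesis 1 as "the prompt will increase the proportion of women counseled on transitioning care to a primary care provider or cardiologist after pregnancy" and tags it as the primary outcome. The Analysis Plan opens in the same way: "We hypothesize that a provider nudge will increase the proportion of women who are counseled about 1) transitioning care".

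**Nudge.** The Design section describes a staff message to the provider of each intervention-arm woman. On its content: "There will be a dot phrase recommending follow-up with primary care or cardiology".

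**Assessment.** Design and Procedures say that two reviewers assess counseling. Procedures adds that they work from the discharge summary and the after-visit summary. Neither section says whether they know the arm. The section on resources for human research protection names a study coordinator as one of the data collectors and also as a possible sender of prompts.

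**Related measures.** Secondary outcome 3 is "Use of scripted dot phrases (available in Epic) for counseling on transitions of care and CVD risk in the postpartum note". Secondary outcome 4 is attendance at a preventive visit within 6 months. On reporting, the Analysis Plan says "Proportion and relative risk (95% CI) will be presented for primary and secondary outcomes"; it describes no analysis linking dot-phrase use to the primary outcome.

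**The concern.** The intervention can act on the measuring instrument as well as on behavior. A provider who receives the message has text at hand with the content that the endpoint looks for. Using it may reflect a real conversation or only a fuller note, and the endpoint cannot tell the two apart.

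Judging whether a chart documents counseling also takes some discretion. A reviewer who knows the arm could, without intending to, score borderline notes differently. The plan does not exclude this, and it does not separate sending prompts from collecting data.

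At stake is the interpretation of the main result. A charting effect, or scoring that is not independent of arm, could be reported as more women counseled.

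**Working it through.** **Step 1. Reproduce the sample size.** Inputs from Accrual and the Analysis Plan: 21% vs 40%, 80% power, two-sided alpha 0.05, 20% not attending. With unpooled variance:

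n per arm = (1.960 + 0.842)² × (0.21×0.79 + 0.40×0.60) / 0.19² = 7.849 × 0.4059 / 0.0361 = 88.25.

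Dividing by 0.80 gives 110.3, rounded up to 111 per arm, total 222. This is the plan's figure. Pooled variance gives 91 per arm and 228 in total, within 3%.

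**Step 2. Set up the illustration.** Attendees per arm = 222 × 0.80 / 2 = 88.8, taken as 89. Assume that true counseling is equal in the two arms, that documentation would otherwise be 21% in each, and that inserted text is present in the scored documents and counts. Let f be the share of otherwise undocumented intervention attendees who gain charted text only. Let s be the fraction of that gain that spills over to controls. The documents give no value for f or s.

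- Intervention rate p1 = 0.21 + 0.79f
- Control rate p0 = 0.21 + 0.79fs
- Otherwise undocumented attendees per arm: 0.79 × 89 = 70.3

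**Step 3. Chance of a significant result** (pooled two-sided chi-square, normal approximation). Example, f = 0.10 and s = 0: p1 = 0.289, mean rate 0.2495. The standard error under no difference is √(2×0.2495×0.7505/89) = 0.0649, and under the alternative √((0.21×0.79 + 0.289×0.711)/89) = 0.0646. Then Φ((0.079 − 1.96×0.0649)/0.0646) = Φ(−0.75), about 0.23.

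| f | women (f × 70.3) | p1 | chance, s = 0 | p0 at s = 0.5 | chance, s = 0.5 |
|---|---|---|---|---|---|
| 5% | 3.5 | 25.0% | 10% | 23.0% | 6% |
| 10% | 7.0 | 28.9% | 23% | 25.0% | 9% |
| 15% | 10.5 | 32.9% | 43% | 26.9% | 14% |
| 20% | 14.1 | 36.8% | 65% | 28.9% | 20% |
| 24% | 16.9 | 40.0% | 79% | 30.5% | 26% |

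Exact binomial enumeration agrees within about one percentage point. If all 111 per arm are counted, with non-attenders as undocumented, the control rate is 0.80 × 21% = 16.8%. The 10% case then compares 16.8% with 23.1% (chance about 22%), and the 24% case 16.8% with 32.0% (about 75%).

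The 24% row is back-solved: 0.19 / 0.79 = 0.241. Its 79% is therefore the planned power restated. It shows only that about 17 women with added text would reproduce the whole planned effect.

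**Step 4. What the table leaves out.** It covers added charting only. The documents give no basis for putting a size on scoring that is influenced by knowledge of the arm.

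**The case against.** **The plan is consistent.** This stands. Documentation is the endpoint wherever it is defined or sized, and Hypothesis 1 is tagged as that outcome. Background likewise uses the word for a chart-based rate: "counseled on follow-up with primary care and only 4% were counseled on CVD risk at their postpartum visits based on chart review". A reader might infer that hypothesis and endpoint contradict each other; the documents do not support that.

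**The mechanism depends on the source.** This also stands. Secondary outcome 3 places dot phrases in the postpartum note, while Procedures lists other documents for the reviewers. Whether these include the note is unclear. If they do not, inserted text may never be scored.

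**Safeguards exist.** There are two reviewers, prompt opening and dot-phrase use are recorded, and 6-month attendance cannot be created by template text. But none of these measures counseling, and none bears on masking.

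**Spillover dilutes the effect.** Randomization is by patient, so one provider may see both arms, and the phrases are available in Epic. The zero-spillover column is the upper case.

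**It is a pilot.** The Abstract says so, but the Analysis Plan declares a superiority trial tested at two-sided 0.05, so the result will be read as evidence of effect.

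**The reviewers are unmasked, or the coordinator is one of them.** A reader might infer either. The documents say neither; they are silent on masking and do not name the reviewers.

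**Conclusion.** The point holds as an inexpensive improvement that should be made. It is not a flaw in the test. Two risks remain: arm-aware scoring of a judgement-based endpoint, and reporting more documentation as more counseling.

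The size is illustrative. Over 5% to 24% added charting, the chance of a significant result is about 10% to 79% without spillover and 6% to 26% with half spillover. These figures rest on assumed rates, on equal true counseling and on the inserted text being scored. A reader might take them as an inflated type I error. They are not false positives for documentation, which really would differ between arms; they bear only on interpreting the result as counseling.

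**What to change.** **(a) Masking.** Give the two reviewers a chart list without arm. Where existing staffing allows, use abstractors who send no prompts, and apply the same rule to both arms. A rule that bars senders only from the charts of nudged women should be avoided: it would tie abstractor to arm and could create the bias that it is meant to prevent.

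**(b) Wording.** State Hypothesis 1, the corresponding sentence in the Analysis Plan and the primary conclusion as documented counseling.

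**Clarifications only.** Before abstraction, fix whether dot-phrase text alone counts as documented counseling, and whether the sources named in Procedures include the postpartum note. Describe the primary outcome by dot-phrase use. This table cannot separate real from template-only counseling, because a real conversation may also be charted with a dot phrase.

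**Cost.** A list without arm, a division of work, a few sentences and one descriptive table. Sample size, recruitment and intervention do not change. There are two downsides: the inserted wording may partly reveal the arm, so masking will be incomplete, and the trial makes a narrower claim.
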